# LIST OF ABBREVIATIONS

AE	Adverse Event/Adverse Experience			
CFR	Code of Federal Regulations			
CRF	Case Report Form			
CRO	Contract Research Organization			
DHHS	Department of Health and Human Services			
DSMB	Data and Safety Monitoring Board			
FDA	Food and Drug Administration			
FWA	Federal Wide Assurance			
GCP	Good Clinical Practice			
HIPAA	Health Insurance Portability and Accountability Act			
ICF	Informed Consent Form			
ICH	International Conference on Harmonisation			
IDE	Investigational Device Exemption			
IND	Investigational New Drug Application			
IRB	Institutional Review Board			
PHI	Protected Health Information			
PI	Principal Investigator			
SAE	Serious Adverse Event/Serious Adverse Experience			
BTA	Botulinum Toxin A			
UTI	Urinary Tract Infection			
OAB	Overactive Bladder			
UUI	Urinary Urgency Incontinence			
PVR	Post Void Residual			
SNM	Sacral Neuromodulation			
PTNS	Percutaneous Tibial Nerve Stimulation			
OAB-Q (LF)	Overactive Bladder Questionnaire (Long Form)			
VAS	Visual Analogue Scale			
PGI-I	Patient Global Impression – Improvement			

# PROTOCOL SUMMARY

Title	Intradetrustor Botulinum Toxin A: Are less injections better?			
Short Title	Bladder Botox			
Protocol Number	KPSC-US-01			
Study Phase	N/A			
Study Site(s)	Kaiser Permanente – Sand Canyon, Kaiser Permanente -Anaheim, UCI			
Number of Subjects	Approx 40 at KPSC, 60 at UCI, 20 at PSJH			
Study Arms	2 arms: One Botox® injection site (study) or 10 Botox® injection sites (control/standard of carl)			
Indication	Overactive Bladder (Urinary urgency and frequency) and urinary urgency incontinence			
Primary Purpose	Our primary objective is to evaluate the efficacy of intradetrusor Botox® for treatment of OAB or UUI based on patient questionnaire scores (OAB-q) in one versus ten Botox® injection [s].			
Overview of Study Design	We plan for a prospective, single-blinded, non-inferiority analyzed, randomized controlled trial. We will evaluate the efficacy, safety, and tolerability of one intradetrusor Botox® injection (study) versus ten injections (control/standard of care). The patient will be blinded . There will be 1:1 randomization.			
Investigational Product Administration	Not applicable, no investigational product.			
Eligibility Criteria	Inclusion criteria: Female, at least 18 years old with diagnosis of overactive bladder (urinary urgency or frequency, OAB) or urinary urgency incontinence (UUI) Exclusion criteria:			
	
 
Have a diagnosis of neurogenic bladder
 
Received intravesical botox injections within prior 6 months
 
Current treatment with either: SNM, PTNS, or OAB medications – need wash out as below
 
SNM – turn device off for at least 2 weeks prior to procedure, off during 3-month follow up window
 
PTNS – no treatments within 2 weeks of start, none during 3-month post-procedure follow up window
 
OAB meds – 2 week wash out period prior to injection, none during 3-month post-procedure follow up window
 
			

	
 
Currently pregnant or trying to get pregnant
 
Contraindications to Botox® - hypersensitivity to Botox®, inability to self-catheterize/refusal to have indwelling catheter
 
Have a UTI (can enroll after treatment)
 
Have urinary retention (PVR>150cc on two occasions)
 
Do not speak English or Spanish
 
		
Study Endpoint	The primary outcome variable will be the OAB-q symptoms severity subscale score (urinary symptom questionnaire) as a marker of efficacy. The secondary outcome variables will include UTI rate, PVR, urinary retention, inter-injection interval, catheter use within 3 months, PGI-I, and VAS pain score.		
Statistical Methods	The target sample size was determined by using the typical standard deviation of the OAB-q score (20 points per literature review) and the known minimally important clinical difference of 10 points of the OAB-q severity subscale, our primary outcome. Using this data, we calculated the sample size of N=102 maximum total (expect to enroll ~40 at KP, ~60 at UCI, ~20 at PSJH), 51 subjects in each arm for a 80% power with 5% significance level. With an estimated 15% lost to follow up rate, we calculated need to enroll 116 subjects.		

# 1 INTRODUCTION

# 1.1 Background

Intradetrusor (bladder) Botulinum toxin A (BTA or Botox®) is a well-established treatment for urinary urgency incontinence (UUI).  While this treatment's efficacy in comparison to alternative therapies including anticholinergic medications and sacral neuromodulation for treatment of UUI has been studied, the ideal number of injection sites within the bladder has not been well established. Intradetrusor BTA injections are often completed as an office procedure while the patient is awake. Each injection site can cause discomfort for the patient during the procedure. Urinary tract infection and urinary retention are risks associated with this procedure and could potentially be related to number of injection sites. Currently, there is a lack of information in the literature regarding the optimal number of intravesical BTA injection sites.

Prior studies evaluated efficacy using 100u BTA spread across 20 injections sites, however current practices at local institutions safely use 10 injections sites based on studies showing similar effect and adverse event profiles between use of 10, 20, and 40 injection sites. Research using animal models has shown diffuse distribution of BTA within the entire detrusor muscle after just a single BTA injection at one site. This has been corroborated in human studies. A recently published observational pilot study shows promise for single site intradetrusor Botox® injection as it reported a lower rate of urinary retention and similar durability. Similar clinical efficacy with only one to three intravesical BTA injection[s] has also been reported.

# 1.2 Hypothesis

We hypothesize that one injection of intradetrusor Botox® will have similar efficacy to ten injections, better tolerability, due to decreased procedure time and less pain, along with potential for lower adverse event rates, specifically urinary retention and urinary tract infections.

2 OBJECTIVES AND PURPOSE

### 2.1 PRIMARY OBJECTIVE

Our primary objective is to evaluate the efficacy of intradetrusor Botox® in an outpatient population based on patient questionnaire scores (OAB-q) in one versus ten Botox® injection [s].

The primary outcome variable will be the OAB-q (urinary symptom questionnaire) symptom severity subscale score. The secondary outcome variables will include UTI rate, PVR, urinary retention, interinjection interval, catheter use within 3 months, PGI-I, and VAS pain score.

# 3 STUDY DESIGN

We plan for a prospective, single-blinded, non-inferiority randomized controlled trial. We will evaluate the efficacy, safety, and tolerability of one intradetrusor Botox® injection (study) versus ten injections (control/standard of care). The patient will be blinded. There will be 1:1 randomization. The physician doing the procedure will not be blinded.

# 3.1 Treatment Arms

There will be two arms for this trial: study arm (one injection) and control arm (10 injections). Across all sites we will plan to enroll 116 maximum participants with anticipated enrollment at Kaiser Permanente being approximately 40 participants.

# 3.2 Study Duration

We anticipate completion of enrollment with approximately 1.5 years. Each subject will participate in the study for 3 months (one 3 week post-procedure visit and one 3 month post-procedure visit). Charts will be reviewed for approximately 6-12 months after procedure completion.

# 4 STUDY PRODUCT INFORMATION

# 4.1 Description

Botox® (onabotulinumtoxina) is an FDA approved treatment of OAB, urinary urgency and frequency, and urinary urgency incontinence via intradetrusor injection. A standard approved dose of 100units will be injected into the detrusor muscle. There is no investigational drug being studied in this trial.

# 4.2 Dosage, Preparation and Administration

The physician will inject 10 mL of (100u/10mL) Botulinum Toxin A in either one or ten sites located in the midline, supra-trigonal posterior bladder wall at a depth of 3mm into the detrusor. Each participant will undergo one injection procedure for the duration of the study.

# 4.3 Toxicity and Safety Information

The most common adverse reactions associated with intradetrusor administration of Botox® include urinary tract infection and urinary retention. These will be monitored as described below in adverse events section.

### 4.4 Concomitant Medications/ Treatments

Current treatment with either: SNM, PTNS, or OAB medications – need wash out as below:

- 1 SNM turn device off for at least 2 weeks prior to procedure, off during 3-month follow up window
- 2 PTNS no treatments within 2 weeks of start, none during 3-month post-procedure follow up window
- 3 OAB meds 2 week wash out period prior to injection, none during 3-month post-procedure follow up window

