### 9.2 Secondary Endpoints

The secondary outcome variables will include UTI rate, PVR, urinary retention, interinjection interval, catheter use within 3 months, PGI-I, and VAS pain score.

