### 12.3 Final Analysis Plan

We will describe the study population, including patient age, race/ethnicity, baseline severity scores (OAB-Q), BMI, medical history (prior surgery, menopausal status, prior Botox, etc.), overall, by arm, and stratified by study site (KPSC, UCI, PSJH). We will summarize continuous measures using means and standard deviations and categorical measures using percentages. We will compare study arms using the t-test or Fisher's exact test, as appropriate.

We will examine the outcome measures (OAB-Q and any secondary measures) to determine whether they are approximately normally distributed. If not, we will apply a

transformation prior to analysis to make the analytic variable approximately normal. If no transformation successfully achieves approximate normality, we will apply non-parametric tests for analysis, including Wilcoxon's rank-sum test instead of the t-test and quantile regression instead of linear regression.

We will analyze the main study outcome (OAB-Q score) initially using a t-test to compare the two study arms, overall and stratified by study site. We will further analyze the outcome using generalized estimating equations to account for correlation within study sites. These models will adjust for any potential differences in age, race/ethnicity, baseline severity scores, or any other baseline measures, and will account for any potential differences between study sites.

Secondary outcomes will be analyzed in the same manner as the primary outcome.

Primary analyses will be performed using intention-to-treat to determine study arm. If multiple individuals are not treated according to the randomization plan, we will perform a sensitivity analysis using as-treated, per-protocol study arms.

For any individuals who are lost to follow-up, we will first compare those individuals who are lost to those who complete follow-up in terms of demographics, baseline characteristics and any outcome assessments prior to the time that they are lost to follow-up. For primary analysis of OAB-Q scores, we will analyze complete data including only those who have completed the follow-up questionnaires within the prescribed timeframes. If more than 10% are lost to follow-up, we will additionally perform multiple imputation in an attempt to capture data of those lost to follow-up.

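### Inter-injection interval has no valid value for a woman who moves to another OAB therapy or is not re-injected by the end of chart review, and the planned t-test and GEE cannot handle either case.

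*Combined protocol and SAP*

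**What the plan says.** Section 9.2 lists the secondary outcomes as "UTI rate, PVR, urinary retention, interinjection interval, catheter use within 3 months, PGI-I, and VAS pain score". No section gives the interval a start, an event, a censoring date, or a rule for a woman who has no further injection.

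Section 4.4 limits the other OAB therapies around the study injection. For drugs the wording is "OAB meds 2 week wash out period prior to injection, none during 3-month post-procedure follow up window". For PTNS it is "none during 3-month post-procedure follow up window", and for SNM "off during 3-month follow up window". The exclusion criteria repeat these limits, so women who used such therapies before the trial can enter after washout. After month 3 the plan neither permits nor forbids them, and it does not say that their use will be recorded.

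Section 4.2 states "Each participant will undergo one injection procedure for the duration of the study", so any next injection falls outside the study procedures. Follow-up for it comes from section 3.2: "Charts will be reviewed for approximately 6-12 months after procedure completion".

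Section 12.3 states "Secondary outcomes will be analyzed in the same manner as the primary outcome". For the primary outcome that means a t-test (or rank-sum test), followed by GEE models. The complete-case and multiple-imputation rules there are written for OAB-Q scores and loss to follow-up. They do not address a woman who is followed but not re-injected.

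**The concern.** A t-test needs one number per woman. The interval exists only for women re-injected while their charts are under review. Two groups have none: women whose effect wore off and who took up a drug, PTNS or SNM instead, and women not retreated at all when review ends.

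Leaving them out selects women by something that happens after randomisation and may depend on arm. Giving them the review-end date treats the first group as still benefiting when they are not. A woman who starts another therapy and is re-injected later does have an interval, but it may partly reflect the other therapy.

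At stake is any statement about how long one site lasts compared with ten. If one site wears off sooner, either handling can hide it, and in a non-inferiority trial drift toward equality favours the new method.

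**Working it through.** **What the plan supplies.** It gives no figure for this outcome, so there is none to reproduce. Its 51 per arm concerns the OAB-q score and does not enter. It also gives no re-injection or rescue rates. Every rate below is an assumption and shows direction and rough size only.

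**Illustration A: women on other therapy have no interval.** Assume early failure in f = 0.30 (one site) and 0.15 (ten sites), retreatment at 4 months after failure and at 9 months otherwise, and a share g of failures going to non-Botox therapy.

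- Mean time to any retreatment = 4f + 9(1 - f). One site: 1.20 + 6.30 = 7.50. Ten sites: 0.60 + 7.65 = 8.25. Difference 0.75 months.
- Mean interval among re-injected women = [4f(1 - g) + 9(1 - f)] / [f(1 - g) + 1 - f].

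| g | One site | Ten sites | Difference |
|---|---|---|---|
| 25% | 7.20/0.925 = 7.78 | 8.10/0.9625 = 8.42 | 0.63 |
| 50% | 6.90/0.85 = 8.12 | 7.95/0.925 = 8.59 | 0.48 |
| 75% | 6.60/0.775 = 8.52 | 7.80/0.8875 = 8.79 | 0.27 |
| 100% | 9.00 | 9.00 | 0 |

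This assumes that every re-injection is seen. A review as short as 6 months would miss one at 9 months.

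**Illustration B: review of variable length.** Assume time to loss of effect is 3 months plus an exponential time with mean m = 6 (ten sites) or 4 (one site). Review ends uniformly between 6 and 12 months (mean 9). A share s of failures, unrelated to timing, goes to other therapy; the rest are re-injected at failure.

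1. Still benefiting at end of review: P = (m/6)(e^(-3/m) - e^(-9/m)). Ten sites: 0.6065 - 0.2231 = 0.383. One site: 0.667 x (0.4724 - 0.1054) = 0.245.
2. True mean benefit time up to end of review: R = 3 + m(1 - P). Ten sites: 3 + 6 x 0.617 = 6.70. One site: 3 + 4 x 0.755 = 6.02. Difference -0.68 months.
3. Re-injected women only: mean = 3 + [m(1 - P) - D]/(1 - P), with D = (m/6)[(m + 3)e^(-3/m) - (m + 9)e^(-9/m)]. Ten sites: D = 2.112, mean 5.575. One site: D = 1.291, mean 5.291. Difference -0.28 months. The share s drops out, so this shrinkage is present **with no rescue at all**.
4. Women with no interval: 1 - (1 - s)(1 - P). Ten sites/one site: 38%/24% at s = 0, 51%/40% at s = 20%, 63%/55% at s = 40%.
5. Rescued women given the review-end date: mean = (1 - s)R + 9s.

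| s, ten sites / one site | Ten sites | One site | Difference |
|---|---|---|---|
| 20% / 20% | 7.16 | 6.62 | -0.54 |
| 40% / 40% | 7.62 | 7.21 | -0.41 |
| 20% / 50% | 7.16 | 7.51 | +0.35 |
| 10% / 40% | 6.93 | 7.21 | +0.28 |

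A simulation on the same assumptions agrees to within 0.01 months. With 20% rescue in the ten-site arm, the sign turns once the one-site share passes (0.68 + 2.30 x 0.20)/2.98 = 38%.

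**Reading the two together.** Omitting women loses much of the difference even without rescue. Assigning the end date avoids that loss only if rescue counts as an event. The event definition and the censoring rule therefore have to be settled together.

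**The case against.** The other side has several good points.

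- **Other evidence on persistence.** A reader might infer that the interval is the only durability measure. It is not: OAB-q and PGI-I are collected at 3 months (section 8.2.1), while other therapies are barred. The interval is only the sole listed efficacy-related outcome going further.
- **No durability claim.** The trial's own hypothesis concerns the 3-week OAB-q change (section 12.1). Similar durability appears in the background as a finding of an outside pilot study. This limits the stakes, but the interval is still listed for comparison between arms.
- **Right event for its name.** A reader might infer that the endpoint uses the wrong event. Re-injection is the correct event for an inter-injection interval. Time to any retreatment is a different, composite outcome, and its absence is not an error in itself.
- **Inference from silence.** No text says that other therapies will be used after month 3, or that women without an interval will be dropped or counted as long-lasting. These are the outcomes left open by an unwritten rule. The case report form (Appendix A) is not in the documents, so some dates may already be abstracted.
- **Steering by an unblinded physician.** Section 3 says only that the physician doing the procedure is unblinded. Nothing says that this physician chooses later therapy, so arm-dependent steering is possible but not shown.
- **Rescue is not the whole cause.** In illustration B, rescue adds nothing when only re-injected women are analysed. Reversal needs rescue to be much commoner in the one-site arm.

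What remains is that no visible text gives these women a valid value, and the planned methods require one.

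**Conclusion.** The point holds for one of seven secondary outcomes. As planned, the interval either omits women according to later treatment or counts some who have lost benefit as still benefiting.

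Under the assumptions of illustration B, a true deficit of 0.68 months for the one-site arm appears as 0.28 (re-injected women only), or as 0.54 or 0.41 (end date assigned, with 20% or 40% rescue in both arms). It becomes an apparent gain of 0.28 to 0.35 when rescue is much commoner after one site. Illustration A gives anything from 0.63 down to 0 out of a true 0.75. The direction rests on the one-site effect wearing off sooner, and the size on rates that the documents do not give.

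A reader might go on to infer that the trial's main conclusion is at risk. The documents do not support that: the primary outcome is read at 3 weeks, inside the restricted window, and neither it nor the sample size depends on the interval.

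**What to change.** - **Section 9.2:** add a secondary outcome, time from the study injection to first OAB retreatment by any route: repeat intradetrusor Botox, or start or restart of an OAB drug, PTNS or SNM. Abstract these dates in the chart review already planned.
- **Section 12.3:** analyse it as time-to-event (Kaplan-Meier and Cox), censoring at the end of each woman's chart review. Record that date for every woman.
- **Inter-injection interval:** keep it as a descriptive outcome, or analyse it with other therapy as a competing event. Report by arm how many women were retreated by each route and how many had no retreatment.
- **Timing:** write these rules before abstraction starts and before any results by arm are seen.

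The cost is some extra abstraction, with no added visits. Two limits remain. Therapy obtained outside the institution may be missed, as already applies to re-injection. The composite also counts a drug start the same as a repeat procedure, which is why the counts by route are needed. No change to permitted treatments is proposed.

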### 5 SELECTION AND WITHDRAWAL OF PATIENTS

### Inclusion Criteria

- 1 Female
- 2 18 years old or greater
- 3 Diagnosis of overactive bladder (urinary urgency or frequency, OAB) or urinary urgency incontinence (UUI)

### Exclusion Criteria

- 1 Have a diagnosis of neurogenic bladder
- 2 Received intravesical Botox® injections within prior 6 months
- 3 Current treatment with either: SNM, PTNS, or OAB medications need wash out as below
- 4 SNM turn device off for at least 2 weeks prior to procedure, off during 3-month follow up window
- 5 PTNS no treatments within 2 weeks of start, none during 3-month post-procedure follow up window
- 6 OAB meds 2 week wash out period prior to injection, none during 3-month post-procedure follow up window
- 7 Currently pregnant or trying to get pregnant
- 8 Contraindications to Botox® hypersensitivity to Botox®, inability to self-catheterize/refusal to have indwelling catheter
- 9 Have a UTI (can enroll after treatment)
- 10 Have urinary retention (PVR>150cc on two occasions)
- 11 Do not speak English or Spanish

### Withdrawal Criteria

Subjects are only receiving one procedure as part of the study, thus would only be withdrawn prior to undergoing the procedure if they had exclusion criteria or voluntarily withdrew.

### 6 STRATIFICATION/ RANDOMIZATION SCHEME

Subjects will be randomized via permuted blocks in a 1:1 fashion to either the study group (1 injection) or the control/standard of care group (10 injections). The pre-assigned randomization by permuted block design will be determined at the time of the procedure by opening of a sealed, opaque envelope containing the group allocation.

# 7 ASSESSMENT OF EFFICACY AND SAFETY

7.1 Adverse Events Reporting

### 7.1.1 Adverse Event Definition

Adverse Event (AE) is any untoward medical occurrence associated with the use of a drug in humans, whether or not considered drug related.

All adverse events, including those that are reported by the patient spontaneously, those the study investigator observes, and those that the study investigator elicits in response to openended questions. Recorded adverse events should be assessed by the study investigator indicating the causal relationship of the event with the study drug and whether it meets the criteria for a Serious Adverse Event.

7.1.2 Time Period and Frequency for Event Assessment and Follow-up

Adverse events will be collected from the procedure date through at least 3 months after the Botox® injection procedure.

7.1.3 Serious Adverse Event Definition

SERIOUS ADVERSE EVENT (SAE) is an adverse event or suspected adverse reaction if, in the view of either the study investigator, meets one or more of the following criteria:

- Results in death
- Is a life-threatening adverse event (places the subject at immediate risk of death from the event as it occurred)
- > Results in inpatient hospitalization or prolongation of existing hospitalization
- Results in a persistent or significant incapacity or substantial disruption of the ability to conduct normal life functions
- ➤ Results in a congenital anomaly/ birth defect
- An important medical event that may not result in death, be life-threatening, or require hospitalization may be considered serious when, based upon appropriate medical judgment, they may jeopardize the patient and may require medical or surgical intervention to prevent one of the outcomes listed in this definition

